10.8 Rules for Immediate Study Review

The following rules will automatically trigger a review by the DSMB to determine if any action should be taken to adjust conduct of the trial:

- Three or more participants experience severe adverse reactions.
- Four or more participants have four consecutive positive urine toxicology screens for opioid use, and have been reevaluated through any means as having moderate to severe opioid use disorder.
- One or more serious, unexpected and suspected adverse reaction (SUSAR).

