16.9 Safety Analysis

Treatment emergent adverse events (AEs), including treatment emergent serious adverse events (SAEs), will be summarized by presenting the number of events, number of participants experiencing AEs, and the severity and relatedness of adverse events by treatment arm. All adverse events will be coded using MedDRA® (The Medical Dictionary for Regulatory Activities). The number and proportion of participants experiencing each treatment emergent AE will be provided overall and by treatment arm. Treatment emergent adverse events will be summarized by System Organ Class (SOC) and Preferred Term (PT). If a participant experiences multiple episodes of an event, then the event is only counted once. Detailed listings of treatment emergent adverse events and non-treatment emergent events in the safety population by treatment arm will be provided and include severity, relationship to study medication(s), and action taken, as available. The criteria for an immediate study review by the DSMB will be monitored closely. These criteria are either (1) three or more participants experience severe adverse reactions; (2) four or more participants have four consecutive positive urine toxicology screens for opioid use,

and have been reevaluated through any means as having moderate to severe opioid use disorder; or (3) one or more SUSAR.

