17.17.2 Safety Monitor / Medical Monitor

The CCC Safety Monitor/Medical Monitor is responsible for reviewing all adverse events and serious adverse events reported. All SAEs will be reviewed within one business day of being reported in the eClinical. The Safety Monitor/Medical Monitor will also indicate concurrence or not with the details of the report provided by the site. Where further information is needed, the Safety Monitor/Medical Monitor will discuss the event with the site. Reviews of SAEs will be conducted in the Advantage eClinical data system and will be a part of the safety database. All AEs are reviewed on a regular basis to observe trends or unusual events.

The CCC Safety Monitor/Medical Monitor will summarize each SAE and will provide a report to the Lead Investigator, Sponsor, and NIDA. If the event meets the criteria for FDA-defined expedited reporting, the CCC safety team and regulatory team will work together to submit an expedited safety report to the FDA. A copy of the expedited report will be submitted to the DSMB through the DSC. A copy of the expedited report will be submitted to Indivior and all participating sites. Other safety reports will be generated and presented at the scheduled Data Safety Monitoring Board (DSMB) meetings.

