23.0 APPENDIX A: ADVERSE EVENT REPORTING AND PROCEDURES

Each participating site's Principal Investigator is responsible for study oversight, including ensuring human research subject protection by designating appropriately qualified and trained study personnel to assess, report, and monitor adverse events.

Definition of Adverse Events and Serious Adverse Events

An **adverse event** (AE) is any untoward medical occurrence in humans, whether or not considered study medication related which occurs during the conduct of a clinical trial. Any change from baseline in clinical status, ECGs, lab results, x-rays, physical examinations, etc., that is considered clinically significant by the Medical Clinician are considered AEs.

Suspected adverse reaction is any adverse event for which there is a reasonable possibility that the study medication/intervention caused the adverse event. A reasonable possibility implies that there is evidence that the study medication caused the event.

Adverse reaction is any adverse event caused by the study medication.

An **adverse event, suspected adverse reaction, or adverse reaction** is considered “**serious**” (i.e., a serious adverse event, serious suspected adverse reaction or serious adverse reaction) if, in the view of either the Medical Clinician or Sponsor, it:

- 1) Results in death: A death occurring during the study or which comes to the attention of the study staff during the protocol-defined follow-up period, whether or not considered caused by the study medication(s), must be reported.
- 2) Is life-threatening: Life-threatening means that the study participant was, in the opinion of the Medical Clinician or Sponsor, at immediate risk of death from the reaction as it occurred and required immediate intervention.
- 3) Requires inpatient hospitalization or prolongation of existing hospitalization.
- 4) Results in persistent or significant incapacity or substantial disruption of the ability to conduct normal life functions.
- 5) Is a congenital abnormality or birth defect.
- 6) Is an important medical event that may not result in one of the above outcomes, but may jeopardize the health of the study participant or require medical or surgical intervention to prevent one of the outcomes listed in the above definition of serious event.

Definition of Expectedness

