Any adverse event is considered “unexpected” if it is not listed in the investigator brochure or the package insert or is not listed at the specificity or severity that has been observed. If neither is available then the protocol and consent are used to determine an unexpected adverse event.

Pregnancy

Any pregnancies that occur while a participant is enrolled in the study will be captured on a pregnancy CRF and not separately reported as an AE or SAE. Women who become pregnant during the active treatment period will be discontinued from further medication administration, referred for medical care, and the pregnancy followed until an outcome is known.

Medical and Psychiatric History

A thorough medical and psychiatric history during the screening phase should record any chronic, acute, or intermittent preexisting or current illnesses, diseases, symptoms, or laboratory signs of the participant, to avoid reporting pre-existing conditions as new AEs and to assist in the assessment of worsening in intensity or severity of these conditions that would indicate an AE. Stable chronic conditions, such as arthritis, which are present prior to clinical trial entry and do not worsen are not considered AEs.

Site's Role in Eliciting and Reporting Adverse Events

Appropriately qualified and trained personnel will elicit participant reporting of AEs and SAEs at each study visit designated to collect AEs. Adverse events (medical and/or psychiatric) assessment will initiate with participant consent and follow-up of ongoing adverse events will continue through resolution or 30 days post last study visit. Study personnel will obtain as much information as possible about the reported AE/SAE to complete the AE/SAE forms and will consult with the Safety Monitor/Medical Monitor as warranted.

Standard reporting, within seven days of the site becoming aware of the event, is required for reportable AEs. Expedited reporting (within 24 hours of the site's becoming aware of the event) is required for reportable SAEs (including death and life-threatening events). Sites are responsible for reporting SAEs to the IRB of record, per the IRB of record's guidelines.

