All serious and unexpected suspected adverse reactions are reported by the Medical Monitor on behalf of the Sponsor to the FDA in writing within 15 calendar days of notification. Suspected adverse reactions that are unexpected and meet the criteria for death or immediately life-threatening also require notification of the FDA as soon as possible but no later than 7 calendar days of notification of the event, with a follow-up written report within 15 calendar days of notification of the event. The Medical Monitor will prepare an expedited report (MedWatch Form 3500A or similar) for the FDA and other regulatory authorities, the Sponsor, NIDA, the DSMB, Indivior and copies will be distributed to all sites. Expedited reports will be placed in the site regulatory files upon receipt. A copy of all expedited reports will be forwarded to the site's local IRB, if required.

[figure not shown]
Reporting to the Data and Safety Monitoring Board

The DSMB will receive listing of AEs and summary reports of all SAEs at a frequency requested by the DSMB, but at least annually. Furthermore, the DSMB will be informed of expedited reports of SAEs.

Participant Withdrawal

The Medical Clinician must apply his/her clinical judgment to determine whether or not an adverse event is of sufficient severity to require that the participant be withdrawn from further study medication administration/study intervention. A physician (MD or DO) who serves in the Site PI or Medical Clinician study role must make the decision to withdraw a participant from study medication. If necessary, a Medical Clinician (MD or DO) may suspend any trial treatments and institute the necessary medical therapy to protect a participant from any immediate danger. A participant may also voluntarily withdraw from treatment due to what he/she perceives as an intolerable adverse event or for any other reason. If voluntary withdrawal is requested, the participant will be asked to complete an End-of-Medication visit to assure safety and to document end of medication outcomes and will be given recommendations for medical care and/or referrals to treatment, as necessary.

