For trials conducted under IND, the CCC Safety Monitor/Medical Monitor or designee will report events to the regulatory authorities if the event meets the definition of an expedited event (21CFR312.32). All SAEs that meet expedited reporting will be reported to the FDA/Regulatory Authorities in writing within 15 calendar days of notification of the CCC. If the SAE also meets the criteria for death or immediately life-threatening, the CCC will notify the FDA/Regulatory Authorities electronically, by phone or by fax as soon as possible but no later than 7 calendar days of notification of the CCC pharmacovigilance team, with a follow-up written report within 15 calendar days of notification of the CCC. The CCC pharmacovigilance team will prepare an expedited report (MedWatch Form 3500A or similar) for the FDA/Regulatory authorities and copies will be distributed to all participating site investigators.

C. Data and Safety Monitoring Board (DSMB)

The NIDA CTN DSMB affiliated with this trial will be responsible for conducting periodic reviews of accumulating safety, trial performance, and outcome data. Reports will be generated and presented for Data and Safety Monitoring Board (DSMB) meetings. The DSMB will receive listings of AEs and narratives of all SAEs at a frequency requested by the DSMB and CCTN, but at least annually. Furthermore, the DSMB will be informed of expedited reports of SAEs. The DSMB will make recommendations to NIDA CCTN as to whether there is sufficient support for continuation of the trial, evidence that study procedures should be changed, or evidence that the trial (or a specific site) should be halted for reasons relating to safety of the study participants or inadequate trial performance (e.g., poor recruitment). This includes the rules for triggering immediate DSMB review, defined as three or more participants experiencing severe adverse reactions; four or more participants have four consecutive positive urine toxicology screens for opioid use, and have been reevaluated through any means as having moderate to severe opioid use disorder; or one or more serious, unexpected and suspected adverse reactions.

Following each DSMB meeting, the NIDA CCTN will communicate the outcomes of the meeting, based on DSMB recommendations, in writing to the study Lead Investigator. This communication summarizing study safety information will be submitted to participating IRBs.

D. Quality Assurance (QA) Monitoring

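### The rules for automatic immediate DSMB review contain no trigger for death or serious overdose that applies regardless of attribution

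*Combined protocol and SAP*

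**What the plan says.** Section 10.8 (Rules for Immediate Study Review) names three findings that send the trial to the DSMB automatically. The same three stand in 16.9 and in Appendix B, 24.2 C.

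1. "three or more participants experience severe adverse reactions" (16.9; in 24.2 C, "three or more participants experiencing severe adverse reactions").
2. At least four participants who each give four opioid-positive screens in a row and are then re-evaluated as having moderate to severe OUD.
3. "One or more serious, unexpected and suspected adverse reaction (SUSAR" (10.8).

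Appendix A supplies the definition behind the first rule: "Adverse reaction is any adverse event caused by the study medication". A suspected adverse reaction needs a reasonable possibility of causation, and an event is unexpected if the investigator brochure or package insert does not list it at the specificity or severity seen.

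Separate provisions govern how the board learns of events:

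- Sites report within 24 hours; Appendix A says this "is required for reportable SAEs (including death and life-threatening events".
- The Medical Monitor reviews every SAE within one business day (17.17.2) and reports events to the Sponsor, NIDA and the DSMB (Appendix A, Sponsor's Role).
- On reports that meet the regulatory definition, 17.17.2 says: "A copy of the expedited report will be submitted to the DSMB through the DSC".
- Appendix A adds: "Furthermore, the DSMB will be informed of expedited reports of SAEs".
- The board reviews accumulating safety data periodically (17.17.1). It receives material on all SAEs as often as it asks, and at least once a year (Appendices A and B).

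**The concern.** Overdose is the harm this protocol discusses most. Section 17.17.5 names it as a known toxicity of the study medication. Sections 4.2.4 and 4.3 expect the risk of opioid overdose to differ by arm, because placebo participants do not have the partial agonist's protection. These statements point in opposite directions: one is a risk of the drug, the other a risk of going without it. A rule that depends on attribution can detect the first. It is poorly suited to the second, because an overdose on placebo is unlikely to be put down to study drug.

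An excess of placebo-arm overdoses is therefore a harm the protocol itself foresees, and its immediate-review rules are not built to pick it up. At stake is how soon the independent board must look when a participant dies or has a serious overdose.

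**Working it through.** No figure in the plan is in question, so the check is to run plausible events through the three rules as written, and then to list what else would bring the event to the board.

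**Step 1. Do the three statements of the rules differ?** No. Sections 10.8, 16.9 and 24.2 C carry the same three items, and none adds death or overdose. The gap is not a slip in one place.

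**Step 2. Which events fire a rule?**

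| Event | Rule 1 (severe adverse reactions, three participants) | Rule 2 (screens plus OUD, four participants) | Rule 3 (one SUSAR) |
|---|---|---|---|
| Fatal overdose on placebo, judged unrelated | Not counted: not an adverse reaction | Not counted as an overdose | No: not suspected |
| Fatal overdose on BUP-Inj, judged unrelated | Not counted | Not counted as an overdose | No: not suspected |
| Death from another cause, judged unrelated | Not counted | Not counted | No: not suspected |
| Serious overdose judged drug-caused and severe, but expected | Counts as one of the three needed | Not counted as an overdose | No: not unexpected |
| Serious overdose, suspected and unexpected | Counts if severe and judged drug-caused | Not counted as an overdose | Yes, on the first event |

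The first three rows are the gap. Repetition does not close it: further events judged unrelated still add nothing to rules 1 and 3. The fourth row is only a possibility, because whether an overdose would be classed as expected depends on the package insert, which is not among the documents.

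**Step 3. Does the protocol insist on attribution for opioid harm elsewhere?** No. Rule 2 has no causality test. Under 10.11.3 any non-fatal overdose leads to unblinding, referral and withdrawal from study medication, whatever its cause. That response is at participant level and does not bring the trial to the board.

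**Step 4. What would still bring an unrelated overdose death to the board?**

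| Route | Attribution needed? | Timing to the DSMB |
|---|---|---|
| Copy of the FDA-defined expedited report (17.17.2; Appendix A) | Yes, for reports on the regulatory definition | Prompt |
| Medical Monitor reports events to the DSMB (Appendix A, Sponsor's Role) | No | No deadline stated |
| Periodic review with all SAEs (17.17.1; Appendix A; 24.2 C) | No | At least annually, more often on request |

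So the board is told and does review. What is missing is a rule that makes it look at once.

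**The case against.** The strongest reply is that the plan pairs attribution-based immediate triggers with mandatory periodic review of all SAEs, and that this is a legitimate design. Every death is an SAE whatever its cause. A physician assesses causality, and the Medical Monitor records whether they concur with the site's report. Rule 3 needs only a reasonable possibility of causation, not proof. The Medical Monitor also looks at all AEs weekly for trends (24.2 B). The board may ask to be unblinded at any time (10.11.2), and it, the Sponsor, NIDA and FDA can suspend enrolment (Appendix A). All of this stands, and it keeps the point small. It does not put a death judged unrelated under any immediate rule.

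Three stronger readings may tempt a reader, and the documents do not support them.

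- *That no review of such deaths is required.* Section 17.17.1 makes periodic safety review the board's duty, and 24.2 C gives it narratives of all SAEs.
- *That the plan leaves open whether the board hears of deaths.* The word expedited is used for the 24-hour site report and also for the regulatory report; 17.17.2, for instance, says "If the event meets the criteria for FDA-defined expedited reporting, the CCC safety team and regulatory team will work together". But the reporting chart in 23.1 is not shown and may settle which is meant. The Medical Monitor's route to the board has no attribution test. Section 17.17 says which events expedited reporting will include, without limiting it to those.
- *That a given number of participants would be randomised before the board acted.* The documents state no meeting schedule beyond the annual minimum and no overdose rate, so any such number would rest on assumptions.

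It can also be said that a chair who may decline to convene the board only moves the discretion elsewhere. That is partly right. Under the proposed rule, though, the prompt look itself is obligatory, and only the full meeting is left to judgement.

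**Conclusion.** The point holds as a gap in the immediate-review rules. Two of the three triggers need attribution to study drug and the third measures worsening opioid use, so an overdose death judged unrelated prompts no immediate DSMB review in either arm. This matters most for the placebo arm, where the protocol expects less protection and where a drug-caused rating is least likely. The event would still reach the board through the Medical Monitor and through periodic review.

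The conclusion about the rules follows from their wording and needs no assumed rate. That a placebo-arm overdose would seldom be called drug-related is a judgement rather than something the documents state. The size of the gap cannot be given in participants or events. It is a low-cost safety improvement to consider, and it has no bearing on the primary analysis, the type I error or the sample size.

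**What to change.** In 10.8, and identically in 16.9 and Appendix B 24.2 C, add a fourth trigger: *any death from any cause, or any overdose meeting an SAE criterion, regardless of arm, attribution or expectedness*. State that the DSMB chair reviews such an event promptly and decides whether the full board meets. Keep the three existing triggers.

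The cost is one added item in three places and a small number of extra ad hoc chair reviews. The documents give no basis for forecasting how many; review by the chair alone keeps the burden low. No new data are needed, since sites already report SAEs within 24 hours.

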10.9 Follow-Up

All enrolled participants will be asked to complete a post-medication phase follow-up visit in Week 16 according to the schedule of assessments (see Table 11.1, Section 11). Given the long-lasting nature of BUP-Inj, there is no tapering possible therefore thorough assessment of side effects and AEs will be completed. Any participant who requests may receive a referral to treatment. There may be cases in which off-site visits may be possible with Lead Team approval. Tracking and locating strategies will be used to ensure the highest possible follow-up rates.

10.10 Discontinuation of Study Intervention

Participants will be withdrawn from further study medication administration if it is clinically determined that continuation may be unsafe or if they become unable to come to clinic for study visits (e.g., they become incarcerated). For example, women who become pregnant during the medication period will be immediately withdrawn from study medication administration. Participants who must start treatment with medications that may interact with BUP will be withdrawn based on clinical judgment. Participants who experience intolerable adverse effects or other physical or psychiatric conditions, regardless of relationship to the study medication, may also be withdrawn from further study medication administration.

The Medical Clinician may determine that a participant's clinical condition has deteriorated during the course of the study to the extent that taking study medication may be possibly unsafe or unwise. Examples of clinical deterioration that might trigger a decision to withdraw the participant from study medication include the following:

- New onset of psychiatric or medical conditions that would require intervention and preclude continued participation in the study (e.g., emergence of psychosis, suicide risk, severe cognitive impairment, or dangerous criminal behaviors)
- Worsening of a pre-existing psychiatric or medical condition that would preclude continued safe participation in the study
- Worsening of substance use disorder or overdose such that a higher level of care is indicated
- Hypersensitivity reaction to the study product
- Requirement for opioid analgesics for general anesthesia for surgery
- Increase in LFT or decrease in platelet test results that may increase participant health risks. This includes any of the following: AST/ALT results >5 times upper limit of normal, total bilirubin >2 times upper limit of normal, or platelets below $75 \times 10^3/\mu\text{L}$

A physician (MD or DO) who serves in the Site PI or Medical Clinician study role must make the decision to withdraw a participant from study medication. Also, participants may decide at any time that they no longer wish to continue to receive medication or participate in the study.

Given the long-term nature of BUP-Inj, a taper is not possible, even if the Medical Clinician determines medication discontinuation is warranted for medical or psychiatric reasons. In the event a participant becomes pregnant during the medication period, the pregnant participant will be immediately discontinued from further study medication administration, referred for obstetric care, and the pregnancy followed until an outcome is known.

In the event a participant is withdrawn from further administration of study medication, referrals to treatment programs or recommendations for medical care will be provided as appropriate. Unless consent is officially withdrawn, study staff will encourage participants who are withdrawn from study medication or who opt out of study medication to continue completing twice weekly visit assessments and complete all study assessments throughout the duration of the medication phase (Weeks 1-12) and the follow-up phase (Week 16). If a clinically significant finding is identified (including, but not limited to changes from participant's baseline status prior to receiving study medication) after enrollment, the Medical Clinician will determine if any change in participant management is needed. Any new clinically relevant finding will be reported as an adverse event (AE) if it meets the definition specified in Appendix A of the protocol.

